A self-report battery will be obtained using Appendix H Follow-Up Data Collection CRF, which will be administered at 3-weeks and 6-weeks post-intervention start.

A follow-up blood draw and synovial fluid aspiration will be completed at 6 weeks. The blood and synovial fluid samples will be processed by MAMC DCI staff as described in the "Sample Processing" section below.

Additionally, a chart review will be completed at 6 weeks to ensure that all related medical visit information is recorded in study documentation (Appendix I). A medical record review will be completed to obtain this information. A study visit is not required on behalf of the participant.

Participants will be evaluated for adverse events at each follow-up time point and any complications will be documented.

Data may be captured in person or remotely (e.g., entered directly into REDCap using a personalized coded link with no log-in required, verbally over the phone with a study team member, etc.). Reminder phone calls, texts, and/or emails will be sent to participants at their preferred contact method indicated on the Intake Form (Appendix B).

The Study Completion CRF (Appendix J) will be completed by a study team member to document the completion or withdrawal of all study participants.

Please see the Study Flow Diagram (Appendix L) for a visual representation of the study procedures.

Missed Appointments and Study Removal:

If a participant misses a scheduled appointment, they will be contacted to reschedule in order to maintain the treatment plan of their assigned study treatment group. In the event that a participant misses an appointment, study staff will make one attempt to reschedule each day on three separate days (for three total attempts to reschedule). If the participant cannot be reached or does not respond/reschedule, they will be removed from the study due to non-compliance.

Specimen Storage and Analysis:

All specimens will be collected, processed, and analyzed according to the recommendations of the respective manufacturer, current laboratory SOPs, or software recommendations. *When possible*, study staff will be blinded to treatment groups.

Molecular analyses will be performed over the following 6 months but may go on longer depending on the scope of assays performed, e.g. orthogonal validation.

Specimen Storage

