In the event that there are significant new findings regarding the therapy that may affect participants' willingness to continue in the study, an information sheet will be provided to all current and past participants. The informed consent document will be amended for future participants.

Following completion of informed consent, the results of the Inclusion/Exclusion CRF will be entered into REDCap, an encrypted, access controlled, password protected electronic data capture and management system housed on a DoD server and maintained by the Uniformed Services University Information Technology (USU IT), and a unique study ID will be generated. This coded study ID will be used on all research data collection forms in place of the participant's name, Department of Defense (DoD) ID, or other protected identifier. No PII will be entered into REDCap.

Please see Appendix R for additional information on REDCap.

13.5 DoDI 3216.02 requires an ombudsman to be present during recruitment briefings when research involves greater than minimal risk and recruitment of Service members occurs in a group setting. If applicable, you may nominate an individual to serve as the ombudsman.

- N/A
- Propose ombudsman

13.6 Withdrawal from Study Participation:

Explain the process for withdrawal and specify whether or not the subjects will be given the opportunity to withdraw their data their data/specimens in the event they wish to withdraw from the study

Participant Withdrawal:

Participants may withdraw from the study at any time without penalty. Participants will be informed that withdrawal will not affect their access to health care that they are otherwise entitled to and it will not affect their military position.

If a participant withdraws from the study, we may retain and analyze all coded/de-identified data collected up to the time of withdrawal if the data is necessary to maintain the integrity of the study. However, no further data will be collected after the date of withdrawal.

Participants may contact the study research coordinator/assistant or Principal Investigator to formally withdraw from the study. Participants will be advised to follow-up with their personal physician if they choose to withdraw.

Withdrawal Without Participant Consent:

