A participant may be withdrawn from the study without their consent if remaining in the study might be dangerous or harmful to them. Participation may also be stopped if the military mission requires it, if they lose their right to receive medical care at a military hospital, if the study is canceled, if they fail to adhere to the protocol and/or therapy plan, or if they display inappropriate behavior towards study personnel.

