15.0 Study Monitoring

15.1 Your study requires either Data and Safety Monitoring Plan (DSMP) or a Data and Safety Monitoring Board (DSMB).

- DSMP
- DSMB
- Both
- Not Applicable

A DSMP should describe the plan to monitor the data to verify that the data are collected and analyzed as specified in the protocol. Include who will conduct the monitoring, what will be monitored, and the frequency of monitoring. It should also include the plan to ensure the safety of subjects

Participant Safety Monitoring Plan:

To ensure the safety of participants the PI will:

1. Monitor the conduct of the protocol per the approved study plan and ensure protection of human participants. This may involve periodic review of medical records and/or research files of enrolled participants.
2. Review and keep abreast of adverse events and protocol deviations that occur during the research.
3. The PI will review and sign adverse event logs/reports, protocol deviation (PD) logs /reports, and continuing reviews (CR)/annual progress reports.
4. If there is concern about the welfare of enrolled participants, the PI will stop the research study in progress, remove individual participants from a study, and take whatever steps necessary to protect the safety and well-being of research participants until the IRB can assess the situation.
5. Ensure that all study team members keep current required human subjects research trainings which require renewal every 3 years.

If an adverse event or protocol deviation occurs, it will be evaluated by the Principal Investigator and appropriate actions will be taken as outlined in Section 16.0 Reportable Events. In the case of an emergency, first responders will be called. In order to address the challenge of early identification of an increased risk of a known adverse event, all adverse event data will be tracked and evaluated.

On-site physicians will monitor the progress and health of the participants alongside our Principal Investigator. Participants can elect to withdraw from the study at any time. Participants may also be taken out of the study at any point if a research provider (or one of their treating providers) determines that it is no longer safe for them to continue with the study. If a participant elects to drop out of the study or is withdrawn for safety reasons, they will resume standard of care treatment with their assigned health provider(s).

Data Monitoring Plan:

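### Data collection stops at voluntary withdrawal with no exception for an ongoing adverse event, so the event's later course and outcome have no planned record

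*Combined protocol and SAP*

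**What the plan says.** Section 13.6 has two sub-headings.

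- Under Participant Withdrawal, on voluntary departure, the team keeps what it has ("we may retain and analyze all coded/de-identified data collected up to the time of withdrawal") and then stops: "However, no further data will be collected after the date of withdrawal". The aftercare named is the participant's own doctor: "Participants will be advised to follow-up with their personal physician if they choose to withdraw".
- Under Withdrawal Without Participant Consent, the protocol says: "A participant may be withdrawn from the study without their consent if remaining in the study might be dangerous or harmful to them". It does not say whether data collection or adverse event follow-up continues.

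Section 15.1 covers both groups: "If a participant elects to drop out of the study or is withdrawn for safety reasons, they will resume standard of care treatment". The same section undertakes to track and assess adverse event data, so as to detect early a rise in known risks.

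Section 10.1 sets the routine safety assessment: "Participants will be evaluated for adverse events at each follow-up time point and any complications will be documented". It also says that "a chart review will be completed at 6 weeks to ensure that all related medical visit information is recorded in study documentation", and that this review needs no visit. It does not say whether the review covers people who have left. A Study Completion CRF documents every completion or withdrawal.

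Section 16.1 requires a 24-hour notice and a full written report within 5 business days for defined unexpected events and unanticipated problems. Expected or unrelated events go on a tracking log that is reported at continuing review or closure.

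**The concern.** A participant may leave because of an adverse event. If leaving also ends data collection, follow-up is cut short by the event itself. Its onset is known, but whether it resolved, worsened or led to an admission is not. This truncation falls on the people most likely to have been harmed, so recorded severity and duration would tend to be understated.

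This matters here for two reasons. The IRB approval memorandum rates the study as greater than minimal risk. Section 9.2 states that the combination of PRP and PBMT has not been applied in humans. Section 14.1 names infection, bleeding, neurovascular damage and venous thrombosis among the PRP risks, and the seriousness of such events may not be clear on the day someone decides to stop.

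**Working it through.** The point rests on the text, so the check follows a participant with an open adverse event through each way out of the study.

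1. **Voluntary withdrawal (13.6, first sub-heading).** The stop on data is explicit and has no safety exception. Read literally, it also bars the week-6 chart review in Section 10.1, although that review asks nothing of the participant.

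2. **Withdrawal by the investigator for safety (13.6, second sub-heading; 15.1).** No bar is stated and no follow-up is required. The participant returns to usual care. Section 15.1 also tells the PI to take the steps needed to protect participants until the IRB can assess the situation, but this does not call for the event's outcome to be recorded.

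3. **Removal after missed appointments (10.1).** After three failed attempts to reschedule, the participant is removed as non-compliant. No check is described on whether an adverse event caused the absence, and nothing is said about later follow-up.

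Next, could another provision supply the later record?

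- **Assessment at follow-up points (10.1, 14.2).** A person who has left has no later follow-up points.
- **Weekly log check-ins and PBMT sessions (10.1).** These help detect an event before departure. They do not run past it.
- **Expedited reporting (16.1).** The clock starts at discovery and is not limited to people still enrolled. It does not create the contact through which a later development would be discovered, and it asks for no outcome report after the 5-day report.
- **Tracking log (16.1).** A listed risk such as infection, if classed as expected, goes here even when serious. Reporting then waits for continuing review, generally every 12 months, or closure. No later outcome report is required.

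No section requires an event to be followed to resolution or stabilisation, sets a safety contact after withdrawal, or extends the chart review to those who have left.

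**Scale.** Section 11.5 gives 150 enrolled and a minimum of 92 after attrition:

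- 150 − 92 = 58
- 58 / 150 = 38.7%

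This is context for the planned loss, not an estimate of the people affected. Section 11.2 counts screen failures in its own enrolment allowance, and the pregnancy test and X-ray come after consent (Section 13.3), so some of the 58 may never be treated. The documents do not say what share leaves because of an adverse event, or how many such events would still be open at departure.

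**The case against.** The strongest defence is that the protocol records more than the sentence on withdrawal suggests. Several stronger readings are tempting, and the documents do not support them.

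- **That the event is never recorded.** Complications are documented at follow-up, all adverse events go to the PI, withdrawal is documented on its own form, and reportable events need a full written report that can fall due after the withdrawal date. Only the course after departure lacks a planned record.
- **That all collection stops for safety withdrawals too.** The sentence sits under voluntary withdrawal. For investigator withdrawal the text is silent, so a stop there would be an inference.
- **That adverse events are looked for at follow-up visits alone.** Weekly check-ins run for 6 weeks, PBMT participants attend 3 times a week for 3 weeks, and on-site physicians monitor participants.
- **That a return to usual care is the whole response to a safety withdrawal.** Section 15.1 also gives the PI a broad duty to protect participants.
- **That the tracking undertaking in Section 15.1 is impossible to keep.** Sections 13.6, 15.1 and 16.1 are in tension, but an investigator could reasonably read the reporting duties as continuing.
- **That a number of affected participants can be derived from the attrition allowance.** It cannot, for the reasons given in the scale check.

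Two further points for the defence stand. No stated aim estimates harms, and an event that causes withdrawal is still counted, so incidence up to departure is not lost. The consent pages and the CRF and log forms are not available for review, so they may already hold an outcome field or terms for contact after withdrawal.

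None of this removes the core. For voluntary withdrawal the protocol states a rule, and an outcome field on a form would not supply the contact needed to fill it in.

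**Conclusion.** The point holds in this form: voluntary withdrawal ends data collection with no safety exception, follow-up after a safety withdrawal is unspecified, and an event open at departure therefore has no planned record of its later course and outcome. The consequence is possible truncation of severity, duration and outcome, not loss of the event itself.

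Its size cannot be quantified from the documents. The conclusion assumes that Section 13.6 is applied as written and that the consent form and unseen appendices do not already provide for follow-up after withdrawal. It is a worthwhile, inexpensive correction to the safety data and does not threaten the biomarker comparisons.

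**What to change.** Amend Sections 13.6 and 15.1, and the consent form if it does not already cover this:

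- Define stopping study treatment and withdrawing from follow-up as separate decisions, recorded separately.
- For participants withdrawn by the investigator, and for those who withdraw with an ongoing adverse event and agree, continue contact about the event by phone and still complete the week-6 chart review. State for how long the contact continues.
- Limit the stop on data collection to participants who decline further contact and access to their records.
- Reconcile Section 13.6 with the tracking undertaking in Section 15.1 and the reporting duties in Section 16.1, so that it is clear what applies after each type of departure.

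The cost is protocol and possibly consent wording, plus a few phone contacts and chart checks. The chart review already needs no visit, and Section 13.4 already foresees sending new safety-relevant information to past participants, so contact after departure is not foreign to the plan.

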14.0 Risks and Benefits

14.1 Risks of Harm:

Identify all research-related risks of harm to which the subject will be exposed for each research procedure or intervention as a result of participation in this study. Consider the risks of breach of confidentiality, psychological, legal, social, and economic risks as well as physical risks. Do not describe risks from standard care procedures; only describe risks from procedures done for research purposes

Diagnostic Imaging:

Knee X-rays will be completed in this study as part of the formal screening procedures. If imaging was completed within one month prior to study enrollment, the previous images may be utilized. There is no known minimal level of radiation exposure that is recognized as being totally free of the risk of causing genetic defects (cellular abnormalities) or cancer. However, the risk associated with the amount of radiation exposure received from this study is considered to be extremely low when compared to the everyday risks.

Blood Draw/Venipuncture and Joint Aspirations

There are also common but minor risks associated with blood draws and joint aspirations. These potential risks include: discomfort, bruising, hematoma, redness, swelling, light-headedness, fainting, nerve damage and, rarely, infection.

Physical Therapy (PT)

Possible risks associated with physical therapy treatment include: worsening of pre-existing conditions, continued and/or increased pain that may limit activities, no improvement in mobility or strength, soreness, or failing during and/or injury from physical therapy exercises and/or performance-based tests.

Platelet-Rich Plasma (PRP)

Risks of the PRP injection include donor site/administration site pain, bleeding, infection, damage to surrounding neurovascular structures, hypersensitive or allergic reaction, venous thrombosis, skin discoloration, inefficacy, and need for further procedures.

Photobiomodulation (PBM) Therapy

The risks associated with PBMT are minimal. PBMT is used by a variety of healthcare practitioners for painful clinical conditions. Mild discomfort may be experienced during the treatment, the treatment should not be "hot", but participants should notify the study team member if they feel any uncomfortable warming. Individuals with neuropathies or difficulty distinguishing changes in skin temperature are at higher risk. Potential research-related risks include damage to eye structures, headaches post-procedure, uncomfortable skin heating or erythema/redness, which are both very rare.

Additionally, any time information is collected for a study, there is a small risk of breach of confidentiality.

14.2 Measures to Minimize Risks of Harm (Precautions, safeguards):

For each research procedure or intervention, describe all measures to minimize and/or eliminate risk of harms to subjects and study personnel

All available measures to minimize risks will be taken in accordance with standard clinic protocols.

The risks associated with diagnostic imaging, ultrasound, and blood draw procedures will be mitigated by using trained professionals that follow industry standards for minimizing these risks.

The laser device will be processed through MAMC Property and safety checked through Healthcare Technology Management and Sustainment (HTMS) before being used. A member of the research team will serve as a clinical laser safety officer (CLSO) to establish and manage the study-specific laser safety program. The designee will work with the MAMC Laser Safety Officer (LSO) and participate in the MAMC Laser Safety Committee (LSC) meetings quarterly to receive proper training. Along with the LSO and CLSO, the PI will ensure that the treatment space meets all regulatory requirements for utilization of a treatment laser, including appropriate signage and use of laser blocking screens to absorb any potential scatter/refraction of light outside of the treatment area.

All applicable study team members will complete a battery of training modules and hands-on training sessions to ensure safe operation of the PBMT device, and compliance with local laser safety requirements and American National Standards Institute (ANSI) standards Z136.1 (Safe Use of Lasers) and Z136.3 (Safe Use Lasers in Health Care). See Appendix T for the laser operator training plan.

Protective eyewear will be worn by all participants and study team members during PBMT treatment sessions to avoid potential eye damage. In the rare occurrence that participants experience uncomfortable warmth over the treatment area during PBMT, the treatment will be modified or stopped.

In order to reduce the risks associated with the injection procedures, the team will ensure proper verification of allergies, standard injection site preparation, sterile instrument use, and standard sterile procedure. Venipuncture and aspirations will be conducted by trained personnel.

In order to protect participant confidentiality, research data will be identified using a unique study ID only, and not by participant name, date of birth, DoD ID, or other similar identifier. Biospecimen will be identified by a separate unique sample ID, and not by any direct identifiers. All available measures allowed by law will be taken by research staff to protect participant confidentiality. See protocol section 14.3 for additional information.

All participants will be evaluated for adverse events at each follow-up visit. All adverse events, regardless of severity, will be reported to the Principal Investigator. Adverse events will also be reported according to the guidelines stated in Protocol Section 16.

14.3

Confidentiality Protections (for research records, data and/or specimens):

Describe in detail the plan to maintain confidentiality of the research data, specimens, and records throughout the study and at its conclusion (e.g., destruction, long term storage, or banking). Explain the plan for securing the data (e.g., use of passwords, encryption, secure servers, firewalls, and other appropriate methods). If data will be shared electronically with other team members/collaborators outside the institution, describe the method of transmission and safeguards to maintain confidentiality. Explain whether this study may collect information that State or Federal law requires to be reported to other officials or ethically requires action, e.g., child or spouse abuse

Upon consenting for the study, participants will be assigned a unique study ID. With the exception of the Informed Consent Form with embedded HIPAA Authorization, and electronic Master List, all research data (both paper and electronic) will be identified using this unique study ID only, and not by the participant's name, date of birth, DoD ID, or other protected identifier.

Paper research forms and source documents will be stored in a locked cabinet inside of a locked room, accessible only by local research staff designated and authorized by the Principal

Investigator. The paper Intake CRF which records participant contact information, Informed Consent Forms with embedded HIPAA Authorizations will be stored separately from the coded paper research forms in a locked cabinet inside of a locked room, accessible only by authorized local research staff.

The coded electronic research data for this study will be stored in REDCap, an encrypted, access controlled, password protected electronic data capture and management system housed on a Department of Defense (DoD) server and maintained by the Uniformed Services University Information Technology (USU IT). The local study team will manage the storage and upload of ultrasound in TeleRay, which is an encrypted and access controlled data platform. No PHI/PII will be entered into REDCap or Teleray. See Appendix R for additional information on REDCap.

The local study team will maintain a separate electronic master List which matches the unique study IDs with participant identifying information. The electronic Master List will be stored separately from the coded electronic research data in a secure, password-protected electronic document, on a government computer and network that requires CAC access, and will never be printed.

At the time of biospecimen collection, participants will be assigned a unique sample ID. A separate biospecimen master key, which matches the biospecimen sample ID to the participant study ID, will not contain any direct identifying information. The electronic biospecimen master key will be stored separately from the study master list and coded electronic research data in a secure, password-protected electronic document on a computer and network that requires CAC access.

All research data and forms (both paper and electronic) will only be accessible by authorized study staff, the IRB of record, the local research office, and applicable governmental agencies as part of their duties and in accordance with federal law (except as stated in the next paragraph). These duties include making sure that research participants are protected.

Musculoskeletal Injury Rehabilitation Research for Operational Readiness (MIRROR), which is based out of the Department of Physical Medicine & Rehabilitation (PM&R) at the Uniformed Services University (USU), is serving as the data coordinating center for this research study. As such, authorized staff from MIRROR/USU will have access to the coded research data that is entered into REDCap. Authorized staff from MIRROR/USU will not have access to the electronic Master List, the paper research records, or any participant PHI/PII.

There will be appropriate data sharing agreements in place.

Any research data shared with an approved agency for review will be linked only to the participant's unique study ID and not with the personal identity of the participant (i.e., name, DOB, DoD ID, address, phone number, etc.). If the research data is used in scholarly presentations or journal articles, the investigators will protect the anonymity of individual participants and report only aggregate data (e.g., group means) where appropriate.

Participants will not be individually identified in any publication or presentation of research results.

14.4

Potential Benefits:

Describe any real and potential benefits of the research to the subject and any potential benefits to a specific community or society

If the individuals in the research are considered experimental subjects (per 10 USC 980), and they cannot provide their own consent, the protocol must describe the intent to directly benefit all subjects

We cannot guarantee that participants will benefit from participation in this research study. The aim of this study is to improve recovery of knee osteoarthritis (KOA), it is expected that all treatment arms will help KOA, some treatments potentially quicker than other more traditional treatment options.

14.5

Privacy for Subjects:

Describe the measures to protect subject's privacy during recruitment, the consent process, and all research activities, etc.

Recruitment, consent conversations, and follow-up research activities will take place in a private setting (e.g., closed clinic room, investigator's office, etc.) to minimize the potential opportunity to be overheard or inadvertently witnessed. Information being collected will be limited to only the minimum amount of data necessary to accomplish the proposed research.

No uniformed service members or supervisors will be present during recruitment and consent discussions.

14.6

Incidental or Unexpected Findings:

Describe the plan to address incidental findings and unexpected findings about individuals from screening to the end of the subject's participation in the research. In cases where the subject could possibly benefit medically or otherwise from the information, state whether or not the results of screening, research participation, research tests, etc., will be shared with subjects or their primary care provider. State whether the researcher is obligated or mandated to report results to appropriate military or civilian authorities and explain the potential impact on the subject

There is the possibility incidental findings could reveal information the participant would not otherwise be aware of. In cases where the participant could possibly benefit medically or otherwise, the participant will be notified and, when appropriate, so will their primary care provider. Research representatives will not share incidental and unexpected findings with anyone else unless required by law.

In cases involving military personnel, information regarding their health may be required to be reported to appropriate medical or command authorities to ensure the proper execution of the military mission, including evaluation of fitness for duty.

Although unlikely, incidental findings could impact a participant's future ability to receive health or life insurance, as is the case with all medical care. Incidental findings may also make the participant feel anxious.

Incidental Findings:

Participants will not have the option to decline receiving incidental findings in this study. The PI will review all incidental findings and determine whether or not the incidental finding should be reported to the participant. The PI will utilize guidance provided by OHRP *Attachment F - Recommendations on Reporting Incidental Finding*. Specifically, the PI will consider whether the findings are validated and actionable, and if they have potential implications for a participant's physical and mental wellbeing. The PI will assume responsibility for notifying participants of incidental findings, explaining the findings, implications, and recommendations for next-steps to follow-up with their clinical care team.

Incidental Findings of Future Studies:

A study team member will transcribe the participants' election from the ICF to opt in/out of receiving results of incidental findings from future research studies in the Master List (Appendix P). This information will also be recorded on the Biospecimen Master Key (Appendix S).

If a participant elects to receive incidental findings of future research studies and they agreed to storage of their identifiable biological specimens, then the principal investigator of the respective research study will be responsible for notifying the participant as indicated by procedures in their study-specific protocol.

If a participant elects to receive incidental findings of future research studies and they did not agree to storage of their identifiable biological specimens, then incidental findings may only be

relayed to the study participant while this protocol is open and the original master list exists. Once the original master list is destroyed, the participant's biospecimens will be completely de-identified and will be unable to be linked back to a specific individual.

